11.4 Documentation

Source documents may include a subject's medical records, hospital charts, clinic charts, the investigator's study subject files, as well as the results of diagnostic tests such as X-rays, laboratory tests, and electrocardiograms. The investigator's copy of the eCRFs serves as the investigator's record of a subject's study-related data.

11.4.1 Retention of Documentation

All study related correspondence, subject records, ICFs, record of the distribution and use of all IPs and copies of eCRFs should be maintained on file for at least 2 years after the last approval of a marketing application in an ICH region and until there are no pending or contemplated marketing applications in an ICH region; or until at least 2 years have elapsed since the formal discontinuation of clinical development of the IP. These documents will be retained for a longer period if required by the applicable regulatory requirements or by an agreement with the sponsor. It is the responsibility of the sponsor to inform the investigator/institution as to when these documents no longer need to be retained.

If the responsible investigator retires, relocates, or for other reasons withdraws from the responsibility of keeping study records, custody must be transferred to a person who will accept the responsibility. The sponsor must be notified in writing of the name and address of the new custodian.

11.5 Labeling, Packaging, Storage, Accountability, and Return or Disposal of Investigational Product

11.5.1 Labeling/Packaging

Run-in and Investigational drug will be packaged and labeled into clinical kits.

For the run-in period, 17 pouches will be packaged in a 2-week clinical kit. Each pouch will contain 2 single-use ampoules to provide a sufficient medication supply for one day.

For the treatment period, 17 pouches will be packaged in a 2-week clinical kit. Each subject will receive 4 kits. Each pouch will contain 2 ampoules to provide a sufficient supply of randomized study drug for one day.

11.5.2 Storage of Investigational Product

The study drugs must be stored in a secure area accessible only to the investigator and his/her designees. Study drug(s) must be refrigerated (2-8°C, Do Not Freeze), protected from light, and secured at the investigational site in a locked container.

11.5.3 Accountability of Investigational Product

The IP is to only be prescribed by the principal investigator or his/her named sub-investigator(s) and is to only be used in accordance with this protocol. The IP must only be distributed to subjects properly qualified under this protocol to receive IP.

The investigator must keep an accurate accounting of the IP received from the supplier. This includes the amount of IP dispensed to subjects, amount of IP returned to the investigator by the subjects, and the amount returned or disposed upon the completion of the study. A detailed inventory must be completed for the IP.

11.5.4 Return or Disposal of Investigational Product

All IP will be returned to the sponsor or their designee or destroyed at the study site. The return or disposal of IP will be specified in writing.

11.6 Recording of Data on Source Documents and Case Reports Forms (CRFs)

All subject data will be captured in the subject source documents which will be transcribed in the eCRFs. The investigator is responsible for ensuring that study data are completely and accurately recorded on each subject's eCRF, source documents, and all study-related materials. All study data should also be attributable, legible, contemporaneous, and original. Recorded datum should only be corrected in a manner that does not obliterate, destroy, or render illegible the previous entry (e.g., by drawing a single line through the incorrect entry and writing the revision next to the corrected data). An individual who has corrected a data entry should make clear who made the correction and when, by adding to the correction his/her initials as well as the date of the correction.

Data entry of all enrolled and randomized subjects will use software that conforms to 21 CFR Part 11 requirements and will be performed only by staff who have been trained on the system and have access to the system. An audit trail will be maintained within the electronic system to capture all changes made within the eCRF database. After the last subject randomized completes Visit 6, the data from Visits 1- 6 will be locked. After final database lock, electronic copies of all applicable Subjects eCRF will be provided to each Investigator's Site to be maintained on file by the Investigator.

11.7 Handling of Biological Specimens

Blood samples may be submitted to one or more central laboratories and / or analytical laboratories for processing, storage and analysis. All laboratories meet Good Laboratory Practice requirements.

11.8 Publications

Authorship and manuscript composition will reflect cooperation among all parties involved in the study. Authorship will be established before writing the manuscript. The study sponsor will have the final decision regarding the manuscript and publication.

APPENDIX 2: PROHIBITED MEDICATIONS

Washout Period	Prohibited Medication/Procedure/Surgery	Examples Examples listed DO NOT include all exclusionary medications/procedure/surgery within each category
72 Hours (prior to V1)	Antihistamines (including ocular) All other topical ophthalmic preparations	Zyrtac, Allegra, Claritin, Benadryl, Sudafed Includes any OTC artificial tear substitutes
7 days (prior to V1)	Contact Lenses	
14 days (prior to V1)	Corticosteroids Mast cell stabilizers (Including ocular)	Hydrocortisone, Advair, Flonase, including EYSUVIST TM Lodoxamide, Nedocromil, Pemirolast, Ketotifen
30 Days (prior to V1)	Oral aspirin or aspirin-containing products that have been taken on UNSTABLE dose. If the subject is taking aspirin or aspirin-containing products, it must be taken on a STABLE dose and the dose cannot change during the study period.	Stable dose is defined as unchanged for at least 1 month prior to the start of Visit 1 and expected to remain unchanged throughout the study
	Unstable** medications known to cause ocular drying. Punctal Plugs (temporary or permanent) Other Investigational Product or Device	The following medication classes: Antidepressants, Anticholinergics, Diuretics, Beta-Blockers

Washout Period	Prohibited Medication/Procedure/Surgery	Examples Examples listed DO NOT include all exclusionary medications/procedure/surgery within each category
45 days (prior to V1)	Systemic corticosteroids (include oral, nasal sprays, and inhalers)	
60 Days (prior to V1)	Cyclosporine-containing drops or lifitegrast ophthalmic solution	Restasis [®] , Cequa [®] , Xiidra [®]
3 months (prior to V1)	Any thermal pulsation treatment	LipiFlow, iLux, MiBo thermoflo, intense pulsed light
12months (prior to V1)	Intraductal meibomian gland probing	LASIK

Abbreviation: OTC = over the counter; V1 = Visit 1

APPENDIX 3: EXAMINATION PROCEDURES, TESTS, EQUIPMENT, AND TECHNIQUES

Visual Acuity Procedures (ETDRS Chart)

LogMAR visual acuity (VA) must be assessed using an Early Treatment Diabetic Retinopathy Study (ETDRS) chart. The procedure used will be consistent with the recommendations provided for using the ETDRS eye chart. VA testing should be done with the subject wearing their most recent correction. If at any visit after Visit 1, more than 10 letters in BCVA are lost compared to screening visit record, then refraction should be performed.

Equipment

The VA chart to be used is the ETDRS chart. If smaller reproduction (18" by 18", e.g., from Prevent Blindness) wall charts are used, the subject viewing distance should be exactly 10 feet (or as specified by the manufacturer). In ALL cases, for purposes of standardizing the testing conditions during the study, all sites must use only the 'R' charts, and the right eye should be tested first. For reflectance (wall) charts, the chart should be placed frontally and well-illuminated.

Measurement Technique

The chart should be at a comfortable viewing angle. The right eye should be tested first. The subject should attempt to read each letter, line-by-line, left to right, beginning with line 1 at the top of the chart. The subject should be told that the chart has letters only, no numbers. If the subject reads a number, he or she should be reminded that the chart contains no numbers, and the examiner should then request a letter in lieu of the number. The subject should be asked to read slowly, so as to achieve the best identification of each letter. He/she is not to proceed to the next letter until he/she has given a definite response.

If the subject changes a response (e.g., 'that was a "C" not an "O"') before he has read aloud the next letter, then the change must be accepted. If the subject changes a response having read the next letter, then the change is not to be accepted. The examiner should never point to the chart or to specific letters on the chart during the test.

A maximum effort should be made to identify each letter on the chart. When the subject says he or she cannot read a letter, he or she should be encouraged to guess. If the subject identifies a letter as 1 of 2 letters, he or she should be asked to choose 1 letter and, if necessary, to guess. When it becomes evident that no further meaningful readings can be made, despite encouragement to read or guess, the examiner should stop the test for that eye. However, all letters on the last line should be attempted as letter difficulties vary and the last may be the only one read correctly. The number of letters missed or read incorrectly should be noted.

LogMAR Visual Acuity Calculations

The last line in which a letter is read correctly will be taken as the base logMAR reading. To this value will be added the number "N x 0.02" where 'N' represents the total number of letters missed up to and included in the last line read. This total sum represents the logMAR VA for that eye.

For Example: Subject correctly reads 4 of 5 letters on the 0.2 line, and 2 of 5 letters on the 0.1 line.

Base logMAR	= 0.1
N (total number of letters incorrect on line 0.2 as well as 0.1)	= 4
N x T (T=0.02)	= 0.08
Base logMAR + (N x T)	= 0.1 + 0.08
logMAR VA	= 0.18

Repeat the procedure for the left eye.

In order to provide standardized and well-controlled assessments of VA during the study, all VA assessments at a single site must be consistently done using the same lighting conditions and same correction if possible during the entire study. If the same correction cannot be used (i.e., a subject forgets his glasses), the reason for the change in correction should be documented.

Slit-Lamp Biomicroscopy Procedures

Slitlamp biomicroscopic observations will be graded as Normal or Abnormal. Abnormal findings will be categorized as clinically significant (findings that may interfere with study parameters or otherwise confound the data as determined by the investigator) or not clinically significant (NCS). The following will be examined:

- Cornea
- Conjunctiva
- Anterior Chamber
- Iris
- Lens
- Eyelid

External magnification and biomicroscopy will be performed using a slit-lamp. Magnification will be consistent with standard clinical practice. The subject will be seated.

Dilated Fundoscopy

Dilated fundoscopy will be performed using indirect ophthalmoscopy. The investigator will make observations of the vitreous, retina, macula, choroid and optic nerve.

Observations will be graded as Normal or Abnormal. Abnormal findings that are clinically significant (as determined by the investigator that may interfere with study parameters or otherwise confound the data) and those that are not clinically significant will be described. A dilated fundoscopy examination should be performed if retinal disease is detected.

- Vitreous: Examination should emphasize the visual axis.
- Retina, Macula, Choroid: Include an observation of the retina and its blood vessels. Eyes should be excluded from the study if active inflammation is present.
- Optic Nerve: Significant damage or cupping to the optic nerve should be noted.

It is recommended that tropicamide 1% ophthalmic solution be used to dilate subjects. The use of cyclopentolate 1% ophthalmic solution is recommended as secondary dilating medication, should the need arise.

Intraocular Pressure

Intraocular pressure will be measured in each eye by contact tonometry by the examiner and the results will be recorded in mmHg. A single measurement is made to obtain a determination of IOP. The same tonometer employing the Investigator's standard technique will be used throughout the study. In addition, all reasonable efforts will be made to have the same examiner obtain all IOP measurements for a given subject.

Ora proprietary scales – Not for distribution without permission

Ora Calibra® Ocular Discomfort Scale for Dry Eye

[figure not shown]
Ora Calibra® Ocular Discomfort & 4-Symptom Questionnaire for Dry Eye

Visual Analogue Scale (VAS)

Subjects will be asked the following questions regarding ocular discomfort (unrelated to study drug instillation) at all visits.

The subject will be asked to rate each ocular symptom due to ocular dryness by placing a vertical mark on the horizontal line to indicate the current level of discomfort. 0% corresponds to “no discomfort” and 100% corresponds to “maximal discomfort.” Subjects are to evaluate their current ocular discomfort symptoms as experienced while completing the questionnaire.

Ocular Surface and Disease Index (OSDI)[®] for Dry Eye

Ocular Surface Disease Index[®] (OSDI[®])²

Ask your patients the following 12 questions, and circle the number in the box that best represents each answer. Then, fill in boxes A, B, C, D, and E according to the instructions beside each.

Have you experienced any of the following during the last week ?	All of the time	Most of the time	Half of the time	Some of the time	None of the time
1. Eyes that are sensitive to light? ..	4	3	2	1	0
2. Eyes that feel gritty?	4	3	2	1	0
3. Painful or sore eyes?	4	3	2	1	0
4. Blurred vision?	4	3	2	1	0
5. Poor vision?	4	3	2	1	0

Subtotal score for answers 1 to 5 (A)

Have problems with your eyes limited you in performing any of the following during the last week ?	All of the time	Most of the time	Half of the time	Some of the time	None of the time	N/A
6. Reading?.....	4	3	2	1	0	N/A
7. Driving at night?	4	3	2	1	0	N/A
8. Working with a computer or bank machine (ATM)?.....	4	3	2	1	0	N/A
9. Watching TV?	4	3	2	1	0	N/A

Subtotal score for answers 6 to 9 (B)

Have your eyes felt uncomfortable in any of the following situations during the last week ?	All of the time	Most of the time	Half of the time	Some of the time	None of the time	N/A
10. Windy conditions?.....	4	3	2	1	0	N/A
11. Places or areas with low humidity (very dry)?	4	3	2	1	0	N/A
12. Areas that are air conditioned?...	4	3	2	1	0	N/A

Subtotal score for answers 10 to 12 (C)

Add subtotals A, B, and C to obtain D
(D = sum of scores for all questions answered) (D)

Total number of questions answered
(do not include questions answered N/A) (E)

[figure not shown]
Please turn over the questionnaire to calculate the patient's final OSDI[®] score.

Evaluating the OSDI® Score¹

The OSDI® is assessed on a scale of 0 to 100, with higher scores representing greater disability. The index demonstrates sensitivity and specificity in distinguishing between normal subjects and patients with dry eye disease. The OSDI® is a valid and reliable instrument for measuring dry eye disease (normal, mild to moderate, and severe) and effect on vision-related function.

Assessing Your Patient's Dry Eye Disease^{1,2}

Use your answers D and E from side 1 to compare the sum of scores for all questions answered (D) and the number of questions answered (E) with the chart below.* Find where your patient's score would fall. Match the corresponding shade of red to the key below to determine whether your patient's score indicates normal, mild, moderate, or severe dry eye disease.

1. Data on file, Allergan, Inc.

Ora Calibra® Conjunctival Redness Scale for Dry Eye

Tear Film Break-Up Time (TFBUT)

The examiner will instill [REDACTED] solution into the inferior conjunctival cul-de-sac of each eye. To thoroughly mix the fluorescein with the tear film, the subject will be instructed to blink several times. In order to achieve maximum fluorescence, the examiner should wait approximately 30 seconds after instillation before evaluating TFBUT.

[figure not shown]
With the aid of a slit-lamp, the examiner will monitor the integrity of the tear film, noting the time it takes to form micelles from the time that the eye is opened. TFBUT will be measured in seconds using a stopwatch and a digital image recording system for the right eye followed by the left eye. A Wratten #12 yellow filter will be used to enhance the ability to grade TFBUT.

For each eye, 2 measurements will be taken and averaged unless the 2 measurements are > 2 seconds apart and are each < 10 seconds, in which case, a third measurement would be taken and the 2 closest of the 3 would be averaged.

Fluorescein Staining

The examiner will instill [REDACTED] solution into the inferior conjunctival cul-de-sac of each eye (fluorescein strips are not allowed). In order to achieve maximum fluorescence, the examiner should wait approximately 3-5 minutes after instillation before evaluating fluorescein staining. A Wratten #12 yellow filter will be used to enhance the ability to grade fluorescein staining. The staining will be graded with the Ora Calibra® Corneal and Conjunctival Staining Scale.

***Ora Calibra® Corneal and Conjunctival Staining Scale for Grading of Fluorescein
Staining***

Lissamine Green Staining

The Investigator will instill [REDACTED] [REDACTED] into the inferior conjunctival cul-de-sac and wait approximately 30 seconds before evaluating staining. The subject will be instructed to blink several times to distribute the lissamine green. The staining will be graded with the Ora Calibra® Corneal and Conjunctival Staining Scale.

Ora Calibra® Corneal and Conjunctival Staining Scale for Grading of Lissamine Green Staining

Unanesthetized Schirmer's Test

Schirmer Tear Test will be performed at least 15 minutes after lissamine green, according to the following procedure:

- Using a sterile Tear Flo Schirmer test strip (Rose Enterprises), a bend in the strip will be made in line with the notch in the strip
- The subject will be instructed to gaze up and in
- The Schirmer test strip will be placed in the lower temporal lid margin of each eye such that the strip fits tightly. Subjects will be instructed to close their eyes
- After 5 minutes have elapsed, the Schirmer strip will be removed. The length of the moistened area will be recorded (mm) for each eye

Drop Comfort Assessments

This procedure will be performed according to Ora, Inc. SOPs and/or guidance documents.

Subject-Reported Drop Comfort Scale

Ora Calibra® Drop Comfort Scale

Subject-Reported Drop Comfort Questionnaire

Ora Calibra® Drop Comfort Questionnaire

[figure not shown]

[figure not shown]
Blood Sampling for Immunogenicity Testing

[figure not shown]
Serum blood draws will be collected at Visits 2, 5, and 6 for immunogenicity testing. Instructions for the collection, handling, and shipping of blood for immunogenicity testing are given in a separate laboratory manual.

[figure not shown]

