15.3 Slit-Lamp Biomicroscopy Examination

A slit-lamp biomicroscopy examination of the cornea, conjunctiva, anterior chamber, iris, lens, and eyelid will be performed at each visit. The results will be graded as Normal, Abnormal Not Clinically Significant (NCS), or Abnormal Clinically Significant (CS). Abnormal findings will be described.

The results will be summarized using counts and percentages for each treatment group at each visit for each eye (study eye and fellow eye). Percentages will be based on the number of subjects in each treatment group with responses. Shift tables for the slit-lamp biomicroscopy parameters will also be provided comparing each follow-up visit to baseline. The worst on-treatment value and the shift from baseline for the worst on-treatment value also will be summarized.

A subject listing of the slit-lamp biomicroscopy parameters will also be produced.

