15.4 Dilated Fundoscopy Examination

A dilated fundoscopy exam will be performed during the study at Day -14 and Day 57, and potentially at unscheduled visit assessments. Observations of the vitreous, retina, macula, choroid, and optic nerve will be graded as Normal, Abnormal NCS, or Abnormal CS. Abnormal findings will be described.

The results will be summarized using counts and percentages for each treatment group at each visit for each eye (study eye and fellow eye). Percentages will be based on the number of subjects in each treatment group with responses. Shift tables for the dilated fundoscopy parameters will also be provided comparing Day 57 to baseline. The worst on-treatment value and the shift from baseline for the worst on-treatment value also will be summarized.

A subject listing of the dilated fundoscopy parameters will also be produced.

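### Slit-lamp and fundus findings are graded clinically significant only by whether they may disturb the study data, so the CS columns of two safety endpoints can understate ocular harm

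*Protocol*

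**What the plan says.** Slit-lamp evaluation and dilated fundoscopy are both listed as safety measures (Protocol 6.2; SAP 2.3). Slit-lamp is done at every scheduled visit, and fundoscopy at screening and at Week 8 or early termination (Protocol Appendix 1).

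The grade is defined in Protocol Appendix 3. For slit-lamp, an abnormal finding is either "clinically significant (findings that may interfere with study parameters or otherwise confound the data as determined by the investigator") or else NCS. For fundoscopy the wording is "Abnormal findings that are clinically significant (as determined by the investigator that may interfere with study parameters or otherwise confound the data"), and the non-significant findings are to be described as well. For the optic nerve there is one further instruction: "Significant damage or cupping to the optic nerve should be noted". It does not say which grade such a finding receives.

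The SAP uses the grade without defining it. Section 15.3: "The results will be graded as Normal, Abnormal Not Clinically Significant (NCS), or Abnormal Clinically Significant (CS"). Section 15.4: "Observations of the vitreous, retina, macula, choroid, and optic nerve will be graded as Normal, Abnormal NCS, or Abnormal CS". The SAP's abbreviation list only spells out CS and NCS. From the grade come counts by visit, shift tables ("Shift tables for the slit-lamp biomicroscopy parameters will also be provided comparing each follow-up visit to baseline"; "Shift tables for the dilated fundoscopy parameters will also be provided comparing Day 57 to baseline") and a shift to the worst value on treatment, each for study eye and fellow eye.

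**The concern.** In a safety table, a reader takes CS to mean that the finding matters for the subject. The Appendix 3 test asks something else: whether the finding may disturb what the study measures. That is a natural question when deciding at Visit 1 whether an eye is suitable for the trial, but the same definition governs every later visit, when the grade has become a safety outcome.

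Two things are at stake. First, a finding that is harmful but does not touch the study's measurements can be placed in the NCS column. Second, if an eye was already Abnormal NCS at baseline, a change from harmless to harmful can stay in that cell and produce no shift. An empty or sparse CS column would then be weaker evidence of ocular safety than it looks.

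**Working it through.** No arithmetic applies; the point depends on no rate, effect size or sample size. The check is to set the definitions side by side and follow typical findings through the tables.

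**How the protocol treats importance in different places**

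| Place | What makes a finding count |
|---|---|
| Appendix 3, slit-lamp and fundoscopy | May disturb study measurements or data, in the investigator's judgement; nothing on harm |
| Exclusion criterion 1 (5.4), Visit 1 only | Need for treatment, and/or possible interference with the study |
| 9.1, adverse events | Any deterioration in a clinical finding that is clinically relevant |
| 9.1, note on visual acuity | logMAR increase of 0.22 or more from baseline |
| 9.2, note on visual threat | Potential damage to the eye; retinal detachment and optic nerve damage are among the examples |

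Only Appendix 3 rests on interference with the study alone. Exclusion criterion 1 has a treatment-need limb that Appendix 3 lacks, and the rules in 9.1 and 9.2 turn on what happens to the subject.

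**Following findings through SAP 15.3 and 15.4**

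1. *New lens opacity or macular change that lowers acuity.* Visual acuity is a study measure (Protocol 6.2), and the OSDI and VAS ask about blurred vision. The investigator can grade this CS, so the table works as intended.
2. *New peripheral retinal tear at Day 57, with acuity, IOP and symptoms unchanged.* Nothing measured is disturbed, so NCS is open to the grader. The table shows Normal to Abnormal NCS: visible as abnormal, but not in the CS column.
3. *Optic nerve Abnormal NCS at baseline, harmful progression by Day 57, with acuity and IOP unchanged.* NCS is again open. The table shows Abnormal NCS to Abnormal NCS, which is no shift.
4. *Harmful finding in the fellow eye only.* Eye-level efficacy uses the study eye alone (Protocol 10.4.2; SAP 8.1), so such a finding has little route to disturbing those data. Yet the fellow eye has its own safety summaries.
5. *Harmless conjunctival finding that makes redness or staining hard to grade.* This meets the definition and may be graded CS.

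**Timing.** Procedures run in the listed order (Protocol 8.4). At Visit 6 (8.4.7), fundoscopy comes after every efficacy examination, with only blood sampling and exit to follow. Whether a finding made at that point may disturb the study is a poor question for a safety outcome.

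Cases 2 to 4 show the gap, and case 1 shows its limit.

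**The case against.** The strongest reply has four parts, and much of it stands.

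- *Study parameters is a broad term.* It is the title of Protocol section 6, which includes acuity, IOP and both eye examinations. The OSDI and VAS add blurred vision and photophobia. The test asks only whether a finding may interfere, and leaves that to the investigator. This stands. A reader might infer that a grader is forced to call retinal, lens or optic nerve findings NCS, or that CS is practically out of reach for most of the structures examined; the text supports neither. The reply does not close the gap, however. Cases 2 to 4 can still be graded NCS. If the two examinations are themselves the parameters, the definition becomes circular. Up to 10 sites may also read it differently, which makes CS counts harder to compare.
- *An NCS finding is still Abnormal.* This stands. A new abnormality shows in the counts, the visit shifts and the worst-on-treatment shift; abnormal findings are described (SAP 15.3 and 15.4) and listed by subject. Only the CS/NCS split, and worsening within Abnormal, can be obscured.
- *Harm is captured elsewhere.* This stands. Protocol 9.1 and 9.2 apply whatever the grade. The weakness lies in these tables and not in safety reporting as a whole. Still, neither document ties a change in CS grade to adverse event assessment, and the examinations are reported as endpoints in their own right.
- *The tables are descriptive, and the rule is the same in both arms under masking.* This stands. No efficacy test depends on them.

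**Conclusion.** The point holds in a limited form. The only definition of CS for two safety endpoints contains no subject-safety criterion, and the SAP builds its tables on it unchanged. A harmful finding that leaves study measurements undisturbed may be graded NCS, and worsening within Abnormal NCS may show no shift. The CS columns can therefore understate ocular harm.

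A reader might go further and infer that the tables would stay clean whatever the drug does. The documents do not support that: new abnormalities remain visible as Abnormal NCS, and clinically relevant deterioration must be recorded as an adverse event.

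The size cannot be computed, because the documents give no rate of such findings. The conclusion assumes that investigators grade by the definition as written; those who grade by ordinary clinical judgement would reduce the effect. Confidence is high that the definition has this gap, and moderate as to how often it would change a grade.

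**What to change.** - In Appendix 3, keep the interference test for the Visit 1 eligibility judgement.
- For safety grading at all visits, define CS by the finding's importance to the subject's ocular health in the investigator's judgement. Reconcile this with the adverse event wording in 9.1 and with exclusion criterion 1, and say how optic nerve damage or cupping is graded.
- State that a post-baseline shift to CS is checked against 9.1.
- Have SAP 15.3 and 15.4 cite that definition.
- SAP section 5 refers to 260 subjects already randomized, so many grades will exist under the present rule. For those, a masked review of the described Abnormal NCS findings before unmasking would show whether any mattered to the subject. Failing that, a table footnote should state the definition used.

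The cost is a few sentences, a site memo and, for existing grades, a short masked review. The downside is a few more findings graded CS and checked against the adverse event log. No examination, sample size or efficacy analysis changes.
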